The Center for Epidemiologic Studies Depression Scale (CES-D) is a depression scale, which will help to assess this co-morbidity. CES-D is a 20-item survey assessing affective depressive symptomatology to screen for risk of depression(Radloff, 1977). Scores range from 0-60, with a score of 16 commonly used as a clinically relevant cut-off (SmarrK.L., 2003). If the CES-D score is > 35 on the V1 baseline survey the study coordinator will obtain more information about the depression (onset, duration, evaluation, hospitalization, treatment, other therapy), and again ask the initial screening questions for risk of suicide.

Traumatic Stress:

The PTSD Checklist for civilians (PCL-C), measures the American Psychiatric Association's Diagnostic and statistical manual of mental disorders (DSM-IV) Criteria B, C, & D of PTSD symptoms based on traumatic life experience either in civilian life, or related to military service, respectively. Seventeen items are rated on a Likert scale with a composite score range of 17 to 85. A score of 44 or higher correlates with probability of civilian-related PTSD (Blanchard, Jones-Alexander, Buckley, & Forneris, 1996).

Fatigue:

Fatigue Severity Scale (FSS) is a nine-item instrument to assess how fatigue interferes with daily activities. Items are scored on a 7-point scale ranging from 1=strongly disagree to 7=strongly agree. Total scores range from 9 to 63 and the higher the rating demonstrates greater fatigue severity (Krupp, LaRocca, Muir-Nash, & Steinberg, 1989).

Quality of Life:

The Quality of Life Scale (QOLS) is a 16-item scale that was modified from a 15-item scale used in chronic disease patients. Topics include different components of daily life such as relationships, community engagement, personal fulfillment, and recreation. Each item is scaled from 1 to 7 and a sum score is calculated to represent higher levels of satisfaction in life (range is 16-112) (Carol S. Burckhardt &

Anderson, 2003; C. S. Burckhardt, Woods, Schultz, & Ziebarth, 1989; Offenbächer, Sauer, Kohls, Waltz, & Schoeps, 2012).

The self-rating health question from the EQ-5D on a scale of 0-100 (0 = worst imaginable health state, 100 = best imaginable health state) will also be administered (Balestroni & Bertolotti, 2012; Rabin & de, 2001).

Social Support:

The Interpersonal Support Evaluation List – Shortened Version (ISEL-12) is a 12-item scale that was modified from a 40-item scale used to assess perceptions of social support. Three dimensions are evaluated: appraisal support, belonging support, and tangible support. Each item is scaled from 1 to 4 for "Definitely True" to "Definitely False." (S. Cohen et al., 1983; S. Cohen & Wills, 1985). Scores are summed and higher scores correlate with more perceived social support.

Cognitive Function:

The Multiple Ability Self-Report Questionnaire (Seidenberg, Haltiner, Taylor, Hermann, & Wyler, 1994) is a self-report questionnaire commonly used to assess perceived cognitive dysfunction. The MASQ has 38 items and assesses five cognitive domains, including language, visual/perceptual ability, verbal memory, visual memory, and attention (Williams & Arnold, 2011).

Mental Health Status:

The Depression, Anxiety, and Stress Scale (DASS-21) is a self-report scale with 21 items (Le et al., 2019; D. Lee, 2019). These questions are divided into three subscales to depression, anxiety, and stress, respectively. The depression subscale scoring ranges from normal (0-9), mild depression (10-12), moderate depression (13-20), severe depression (21-27, and extremely severe depression (28-42). The anxiety subscale scoring ranges from normal (0-6), mild anxiety (7-9), moderate anxiety (10-14), severe anxiety (15-19), and extremely severe anxiety (20-42). The stress subscale ranges from normal (0-10), mild stress (11-18), moderate stress (19-26), sever stress (27-34), and extremely severe stress (35-42). This scale is routinely used in COVID-19 (Wang et al., 2020) and SARS literature (McAlonan et al., 2007).

Work Engagement:

The absenteeism and presenteeism questions of the World Health Organization's Heath and Work Performance Questionnaire (HPQ) will be administered to gauge work engagement. This abbreviated subset of questions includes 11 questions for worked time (Kessler et al., 2004; Kessler et al., 2003)

Healthcare Utilization:

Hospitalizations, emergency department, urgent care and clinic visit counts will be collected for the prior 3 months at enrollment, and then throughout follow-up.

COVID-19:

Questions about COVID-19 experience, exposure, and demographics will be collected. These details will allow us to characterize the population and decide if there is any correlation between exposure status (i.e. working in a particular high risk area) and symptom scores.

Heart Rate (HR), and Heart Rate Variability (HRV):

Continuous heart rate will be recorded while the participant is breathing normally in seated position for 10 minutes using Faros 180 heart rate monitor (Bittium Corporation, Oulu, Finland). Beat to beat intervals (RRI) files will be generated at 1000 Hz via the data acquisition software. The files will be analyzed with Nevrokard HRV software (by Nevrokard Kiauta, d.o.o., Izola, Slovenia). The recordings will be visually inspected to ensure data quality (dropped beats or gross motion artifacts are excluded) and the first 5 minutes of usable tracings will be analyzed. Measures of heart rate variability (HRV) in the frequency domain will be derived and these measures will be integrated over specified frequency ranges (LF: 0.04-0.15 Hz; HF: 0.15-0.4 Hz). Power of RRI spectra in LF, HF range (LF_{RRI} and HF_{RRI}) and total power (TP) will be calculated in normalized units and the ratio of LF/HF will be used as a measure of sympathovagal balance. ("Heart rate variability: standards of measurement, physiological interpretation and clinical use. Task Force of the European Society of Cardiology and the North American Society of Pacing and Electrophysiology," 1996). Data are saved to Excel spreadsheets for further statistical analysis by study team members.

Exploration for Unexpected Barriers, Challenges, or Detrimental Factors:

A REDCap element will be added to data collection at V3 and V5, the final official data collection visit, seeking input regarding any challenges or barriers faced during the study related to factors such as availability of session dates or times, restrictive guidelines for when sessions need to occur, tasks performed during data collections, comfort of the session chair/equipment, difficulty sitting still, office location and accessibility trouble, competing other therapeutic modalities, length of the research study, or any other issues.

Analytical Plan:

Data will be analyzed using the most recent versions of SAS (SAS Institute, Inc., Cary, NC) or the R Statistical Computing Environment. Histograms and descriptive statistics will be examined to evaluate the distribution of study outcomes. Mean contrasts will be used to compare the changes in symptom scores for the primary outcome of Perceived Stress Scale from V1 to V3 in the early intervention vs. delayed intervention groups, as well as secondary and exploratory outcomes/symptom scores. Linear mixed models, which can accommodate within-subject correlations due to repeated assessments over time, may also be used to generate point estimates for effect size along with 95% confidence intervals to support a future larger study if the results in this study do not support immediate clinical application, and potentially for other studies examining other outcomes or potentially more select samples. The association of outcome measures with baseline participant characteristics will also be explored.

Human Subjects Protection:

Subject Recruitment Methods:

Subjects will be recruited by physician referral, word of mouth, and through advertisement (elevator ads, posters, flyers, table outside cafeteria, video overview of study, etc.).

Informed Consent:

The research staff will obtain written informed consent or assent from each competent subject.

Subject Communication Methods:

Participants will be contacted by phone, email, and texting during the study. The study team is going to explore texting for appointment reminders and rescheduling.

Videoconference Data Collection Visit Alternative:

During this time of COVID-19, institutionally approved videoconferencing platforms might be used to interact with study subjects. In person visits are preferred, but in case of office closures or safety reasons the study team might collect data collections through REDCap and videoconferencing.

Confidentiality and Privacy:

Confidentiality will be protected by collecting only information needed to assess study outcomes, minimizing to the fullest extent possible the collection of any information that could directly identify subjects, and maintaining all study information in a secure manner. Per institutional policy, all research study participants will be assigned a hospital MRN number, if none already exists. To help ensure subject privacy and confidentiality, only a unique study identifier number, and first name will appear on the data collection form. Any other collected patient identifying information corresponding to the unique study identifier will be maintained on a separate master log. The master log will be kept secure, on a separate, limited access user group on a shared network drive, with access limited to designated study personnel. Following data collection, subject identifying information will be destroyed at the earliest opportunity, consistent with data validation and study design, producing an anonymous analytical data set. Data access will be limited to study staff. Data and records will be kept locked and secured, with any computer data password protected. No reference to any individual participant will appear in reports, presentations, or publications that may arise from the study.

Brain State Technologies, LLC (BST) may assist with brain pattern review and analysis. To accomplish this, BST is provided with the first 8 characters from the randomly generated, 36-character identifier that the HIRREM software generates for each participant's brain frequency and amplitude data, along with the participant's age and gender, which are believed important for understanding brain patterns. No other participant-specific information is provided.

Safety:

Based on experience reported by Brain State Technologies/Cereset, garnered from provision of case management support, feedback from their clients (now reported to be about 130,000), and feedback

from the HIRREM provider community, as well as results from IRB-approved studies at WFSM (now over 600 participants to receive HIRREM), we are not aware of any serious adverse events resulting from HIRREM sessions.

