Cereset Research to Reduce Stress in Healthcare Workers in the Time of COVID-19

Brief Title: Cereset Research In Healthcare Workers During COVID-19

08/02/2022

NCT04682197

Title:

Cereset Research to Reduce Stress in Healthcare Workers in the Time of COVID-19

Principal Investigator:

[name], MD¹ Department of Neurology Wake Forest School of Medicine [name] E-mail: [contact] [contact] [contact]

Funding: The Susanne Marcus Collins Foundation, Inc.

Key Words: stress, anxiety, COVID-19, Coronavirus, neurotechnology, autonomic dysregulation, acoustic stimulation, neuromodulation, hyperarousal, brain electrical activity, wellbeing, allostasis, HIRREM, Cereset Research

Abstract:

This study will enroll up to 166 healthcare workers, age 18 or older, who have symptoms of stress with a goal of 138 to complete the intervention. Participants will be randomly assigned to either an Early Intervention (EI) group which will receive 4 CR sessions of audible tones echoing current brainwave activity, following enrollment, or a Delayed Intervention (DI) group which will continue current care only and will serve as a control group. Participants in both groups will continue their other current care throughout the study.

The primary outcome will be change in stress as measured by the Perceived Stress Scale (PSS). Secondary outcomes to be collected include symptom inventories for insomnia (Insomnia Severity Index, ISI) and anxiety (Generalized Anxiety Disorder-7, GAD-7). Exploratory measure include depression (Center for Epidemiological Studies- Depression Scale, CES-D), traumatic stress (PTSD Checklist for civilians, PCL-C), overall quality of life (QOLS), social support (ISEL-12), the Multiple Ability Self-Report Questionnaire (MASQ) for cognitive function, Fatigue Severity Scale (FSS) for fatigue, and mental health (Depression, Anxiety, and Stress Scale, DASS-21). Details about COVID-19 status, interaction, workplace engagement, healthcare utilization, and exposure will be collected. Pre- and post-intervention data collection of physiological parameters (Heart rate, HR, and measures of autonomic cardiovascular regulation assessed by heart rate variability) will also be assessed as exploratory outcomes.

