- Current, significant symptoms of long-COVID.
- Current medical student.

Participants will be asked to report use of alcohol, recreational drugs, CBD products, chiropractic, cranial-sacral therapy, and bio-energy work during the intervention, and until V3 and then for the crossover group at V4 and V5.

Sample Size:

Up to 166 participants might be enrolled to get the target sample of 138 to complete intervention. With this target sample size, the study will have 80% power with alpha of 0.05 to detect a clinically meaningful change in the perceived stress scale of 3 points, assuming PSS standard deviation similar to our Cereset Research exploratory study preliminary data (SD 5.62 for difference in PSS from V1 to V3). The clinically meaningful change of 3 points on the PSS was selected based on literature regarding clinically meaningful change in this scale, clinical experience of the investigators, and because this magnitude of change, if detected, would be clinically significant enough to warrant clinical implementation as the immediate next step. The selected target difference in the primary outcome is slightly higher than a minimally important difference of 2.19 to 2.66 points(Drachev et al., 2020), but it is greater than an established clinically relevant difference of 4 points demonstrated in a clinical sample(Plantinga, Lim, Bowling, & Drenkard, 2017). In addition to evaluating the primary question about whether the intervention results in a 3 point improvement in PSS scores at 4-7 weeks post intervention compared to waitlist controls, the study will also explore for potential targets for future research, including those taking selected medications, and those with comorbid conditions or symptoms of interest.

Intervention and Interactions:

Participants will be randomly assigned to either an Early Intervention (EI) group which will receive 4 CR sessions of audible tones echoing current brainwave activity following enrollment, or a Delayed

Intervention (DI) group which will continue current care only and will serve as a control group through the V3 follow-up visit. Participants in both groups will continue their other current care throughout the study.

Schedule of Activities

		Intervention (4 Sessions over 10 calendar days)		Post Interventio	n Data Collection	Crossover Intervention (4 sessions over 10 calendar days)		on)	Crossover Post Inter (DI gr	vention Data Collection oup oly)			

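### The stated 80% power does not follow from its own inputs: 138 participants, a 3-point difference and an SD of 5.62 give about 88%, and 80% needs about 114.

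*Combined protocol and SAP*

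**What the plan says.** The Abstract plans enrolment of up to 166 healthcare workers, "with a goal of 138 to complete the intervention". The Sample Size section repeats this: "Up to 166 participants might be enrolled to get the target sample of 138 to complete intervention". It then states the power: "With this target sample size, the study will have 80% power with alpha of 0.05 to detect a clinically meaningful change" of 3 PSS points, with the SD taken to be similar to that in the exploratory Cereset study, namely "SD 5.62 for difference in PSS from V1 to V3".

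The same section makes clear that the 3 points are a difference between groups, asking "whether the intervention results in a 3 point improvement in PSS scores at 4-7 weeks post intervention compared to waitlist controls". The Analytical Plan matches: "Mean contrasts will be used to compare the changes in symptom scores for the primary outcome of Perceived Stress Scale from V1 to V3", early versus delayed intervention. On allocation, the Intervention and Interactions section says only "Participants will be randomly assigned to either an Early Intervention (EI) group" or a delayed group. The allocation ratio, the sidedness of the test, the dropout rate and the sample size formula are not stated.

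**The concern.** A two-group comparison of mean change has five linked quantities: sample size, difference, SD, alpha and power. Any four fix the fifth. The protocol states all five, and the power implied by the other four is not the one it gives.

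Two things depend on this. First, the recruitment target: if 114 are enough, 138 carries 24 participants of slack; if the trial was really sized on a larger SD, it carries none, and a modest shortfall would take power below 80%. Second, the reading of a null result, which depends on what the trial was designed to detect and with what probability. The section also says that a 3-point effect would justify clinical implementation as the next step, so its design basis should be traceable.

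**Working it through.** **Inputs**
- Difference between arms: δ = 3 (Sample Size).
- SD of V1-to-V3 change: σ = 5.62 (Sample Size).
- Total analysed: 138 (Sample Size, Abstract). Dropout has already been removed: (166 − 138)/166 = 16.9%.
- Alpha: 0.05 (Sample Size). Two-sided is assumed.
- Allocation: 1:1 is assumed, so n = 69 per arm.
- Stated power: 80%.

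**Step 1. Power with 138, normal approximation**
- Standard error of the difference = σ√(2/n) = 5.62 × √(2/69) = 0.957.
- δ/SE = 3/0.957 = 3.135.
- Power = Φ(3.135 − 1.960) = Φ(1.175) = 88.0%.
- With the noncentral t distribution (two-sample t-test), power is 87.6%.

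The stated 80% is not reproduced; the gap is 7.6 points.

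**Step 2. Sample size for 80%**
- n per arm = 2(1.960 + 0.842)²σ²/δ² = 2 × 7.849 × 31.58/9 = 55.1, so 56 per arm, 112 in total.
- The t-test solution is 56.07, so 57 per arm, 114 in total.
- 138 − 114 = 24, or 17% of 138.

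**Step 3. What 138 and 80% would imply (t-test)**
- With σ = 5.62, the difference detectable at 80% is 2.70 points.
- With δ = 3, the SD that gives exactly 80% is 6.245.

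**Step 4. Readings that might rescue 80%**

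| Change to the assumptions | Result |
|---|---|
| One-sided alpha 0.05 | power 93.0%; 45 per arm is enough for 80% |
| Allocation 1.5:1 | power 86.2% |
| Allocation 2:1 | power 83.5% |
| Allocation 2.5:1 | power 80.3% |
| Wilcoxon test, efficiency 0.955 | about 118 in total for 80% |
| Wilcoxon test, worst-case efficiency 0.864 | about 130 in total for 80% |
| All 166 analysed | power 92.8% |

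Only an allocation near 2.5:1 gives 80%, and the protocol contains no such ratio.

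**Step 5. Where 138 could have come from (conjecture; none of these is stated)**
- *A different SD.* Table 1 gives a single-visit PSS SD of 6.3 at V1. With 6.3 in place of 5.62, power at 138 is 79.3% (79.9% by the normal approximation).
- *A different alpha.* Two-sided 0.025 with SD 5.62 needs 68 per arm, 136 in total.
- *Dropout allowed for twice.* 114/0.83 = 137.3 and 138/0.83 = 166.3, close to the protocol's 138 and 166.

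**The case against.** The strongest reply is that the error does no harm. On the stated inputs the trial is better powered than it claims, so an understated power makes a null result look less conclusive than it is, not more. The estimand, the type I error, the analysis and the risk to participants are unaffected. That stands, and it makes this a fault of reporting and traceability, not of design.

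Second, it need not be the SD, the alpha or the power that is misreported. If dropout was allowed for twice, all three are genuine design inputs and the 80% is attached to an already inflated number. That is a fair possibility, and the documents do not decide between it and the others. It does not rescue the sentence, which claims 80% for 138.

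Third, the protocol says the SD is *similar to* the exploratory value. If 5.62 came from the 89 participants with a V3 PSS in Table 1 (an assumption), its 95% interval is about 4.9 to 6.6, which includes 6.245. An SD near 6.25 is therefore plausible. But 5.62 is the only planning value given, and a margin for its uncertainty would have to be stated.

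Fourth, the check assumes equal allocation and a two-sided test. The results for other choices are shown above, and no choice that the documents support gives 80%.

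**Conclusion.** The concern holds. With 69 per arm, a two-sided alpha of 0.05, a 3-point difference and an SD of change of 5.62, power is 87.6% (88.0% by the normal approximation), not 80%. Power of 80% needs 114 analysed (112 by the normal approximation), not 138.

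The result rests on equal arms, a two-sided test, and 138 being the number analysed at V3. The last is itself unclear: the target counts people who complete the intervention, yet the delayed group has received no sessions by V3.

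The error is conservative on the stated inputs, so the recruitment target need not change on this account. If the trial was in fact sized on an SD of about 6.3, power at 138 is about 79% and there is no margin for a shortfall. The documents do not allow a reader to tell which case applies.

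**What to change.** Keep the recruitment target and correct the power sentence in the Sample Size section. If 5.62 is the planning SD, it could read:

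> With 138 participants providing a V3 PSS (69 per arm, 1:1 allocation), a two-sided alpha of 0.05 and an SD of 5.62 for the V1-to-V3 change, power is 88% for a between-group difference of 3 points and 80% for a difference of 2.7 points.

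If 138 came from another SD, another alpha or a second dropout allowance, state that input instead and give the power that follows from it. In either case, state the allocation ratio, the sidedness, the dropout rate linking 138 to 166, and the formula or software. Define the 138, here and in the Abstract, as participants with a V3 PSS.

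The cost is one reworded paragraph and a matching phrase in the Abstract. No change to participants, visits or procedures follows.

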Event	Enrollment (V1) Baseline Data Collection	Baseline Recording and Session 1 (E1) { Within 0-7 days of V1 }	Session 2 (E2)	Session 3 (E3)	Session 4 (E4)	Post Intevention (V2) Data Collection {Within 0-14 days of E4/10-21 days post enrollment}	Post Intervention (V3) Data Collection {Within 4-7 weeks of V2}	Crossover Baseline Recording and Session 1 (D1) {Within 3 months of V3}	Crossover Session 2 (D2)	Crossover Session 3 (D3)	Crossover Session 4 (D4)	Post Intervention (V4) Data Collection {Within 0-14 days of final D4 Intervention}	Post Intervention (V5) Data Collection {Within 4-7 weeks of (V4) data collection}
Informed consent	х												
Demographics	х												
Perceived Stress Scale (PSS) - Standard	х						x						х
Perceived Stress Scale (PSS) - Since last data collection						x						x	
Insomnia Severity Index (ISI) - Standard	х						x						х
Insomnia Severity Index (ISI) - Since Since last data collection						x						X	
Center for Epidemiological Studies Depression Scale (CES-D)						x	x					x	х
Generalized Anxiety Disorder 7-Item (GAD-7) - Standard							x						х
Generalized Anxiety Disorder 7-Item (GAD-7) - Since last data collection						x						x	
PTSD Checklist for Civilians (PCL-C) - Standard	х						x						х
PTSD Checklist for Civilians (PCL-C) - Since Since last data collection						х						x	
Fatigue Severity Scale (FSS)	x					х	x					х	х
Quality of Life Scale (QOLS)	х					х	x					х	х
Interpersonal Support Evaluation List (ISEL-12)	х					x	x					х	х
Multiple Ability Self-Report Questionnaire (MASQ)	х					x	x					х	х
Depression, Anxiety, and Stress Scale (DASS-21)	х					x	x					х	х
EQ-5D Self-Report Health State Question	х					x	x					х	х
WHO's Heath and Work Performance Questionnaire (HPQ)	х						x						х
Healthcare Utilization	х						x						х
COVID Questions	х					x	x					x	x
COVID Healthcare Worker Study Barriers to Participation Survey							x						х
FAROS HRV Recording	x					x	x					x	х
Randomized {EI=Early Intervention DI=Delayed Intervention }	х												
Cereset Research Intervention		X	Х	х	Х			Х	х	х	х		
Study Coordinator Data Entry	х					х	x					x	х
Technologist Data Entry		X	X	X	Х			Х	X	х	Х		

Cereset Research – COVID-19 Study Flow Chart:

Crossover DI Group

Crossover:		V4 Within 0-14 days of final		V5 Within 4-7 weeks of V4
-Short baseline recording		intervention session (up to 45 minutes)		(up to 45 minutes)

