If someone has a 10 point or greater increase in depression (as measured by the CES-D) at a follow up visit, they will be given a community resources handout for mental health. The increase is one standard deviation from the typical drop from baseline in the Exploratory Study.

The manufacturer of Cereset Research recently provided the following update regarding safety and regulatory status:

"This technological approach has been used across several branded versions in what are now about 130,000 individuals, with no serious adverse events reported. The device now branded as Cereset, which will be used in research studies as Cereset Research, uses the same core technology and approach as HIRREM, echoing brainwaves in real time as audible tones. Cereset is commercially available as a wellness technology to help manage stress, restore hope, and achieve restful sleep. Cereset software was tested hundreds of times in our office before going to production beginning in October of 2017.

Since then, thousands of sessions using Cereset software have been provided clinically in 25 other offices across the country without any issues. Results thus far have exceeded our expectations.

We previously shared that the HIRREM equipment used at WFSM since 2011, was registered with the FDA as a Class 2 device under regulation number 21 CFR 882.5050 (biofeedback device), and was thus exempt from FDA 510(k) pre-market notification procedures. Based on the same core technology, with a well-documented, extremely favorable risk profile for this approach, the same applies for Cereset. Importantly, Cereset now falls under more recent FDA guidance provided in a document issued on July 29, 2016, regarding General Wellness: Policy for Low Risk Devices. As a low-risk, general wellness device, Cereset is exempt from FDA regulation. Versions of Cereset Research are currently being used as part of IRB-approved research studies at the Uniformed Services University for Health Sciences, and Womack Army Medical Center, as well as at WFSM (as HIRREM-SOP)." ([name], CEO, Brainstate Technologies/Cereset, February 10, 2019, personal communication).

Participant Compensation:

Participants in this research project will not receive any monetary compensation.

Data and Safety Monitoring:

The principal investigator will be responsible for the overall monitoring of the data and safety of study participants. The principal investigator will be assisted by other members of the study staff.

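### As read from the PDF, the Schedule of Activities has no V1 mark for the GAD-7 or the CES-D, although the text relies on a V1 score for both

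*Combined protocol and SAP*

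**What the plan says.** The Schedule of Activities opens its visit columns with "Enrollment (V1) Baseline Data Collection". The GAD-7 has two rows. "Generalized Anxiety Disorder 7-Item (GAD-7) - Standard" is marked at V3 and V5, and "Generalized Anxiety Disorder 7-Item (GAD-7) - Since last data collection" at V2 and V4. The CES-D has one row, marked at V2, V3, V4 and V5. The V1 cell is empty in all three.

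The text relies on V1 values in several places:

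- The Abstract names the ISI and the GAD-7 as the secondary outcomes and says they will be analysed in a similar way to the V1-to-V3 change in PSS.
- The Analytical Plan compares changes in PSS "from V1 to V3 in the early intervention vs. delayed intervention groups, as well as secondary and exploratory outcomes/symptom scores".
- Exploratory Measures, under Depression, sets out what the coordinator does "If the CES-D score is > 35 on the V1 baseline survey".
- The safety text adds a further step "If someone has a 10 point or greater increase in depression (as measured by the CES-D) at a follow up visit".

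The Outcome Measures section does not list instruments by visit. It sends the reader to Appendix A and the Schedule of Activities.

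**The concern.** The schedule is the table from which a visit form would normally be built, and it is one of the two places to which the text points for visit content. Appendix A lists the instruments without visits, so only the schedule assigns each scale to a visit. If the V1 form was built from a schedule with these cells blank, the enrolment visit would omit both scales. Sessions in the early intervention arm begin 0 to 7 days after V1, and a pre-treatment score cannot be recovered once they have started.

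The change analysis of one of the two secondary outcomes would then be at stake. So would the operation of the V1 depression check, which includes repeating the suicide-risk screening questions.

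**Working it through.** No sample-size or power figure enters this point. The check is a column count followed by a comparison with the text.

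**1. Columns.** The schedule has 14: the event label, V1, four early-intervention sessions, V2, V3, four crossover sessions, V4 and V5 (1 + 1 + 4 + 2 + 4 + 2 = 14).

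**2. Marks by visit.**

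| Row | V1 | V2 | V3 | V4 | V5 |
|---|---|---|---|---|---|
| PSS, ISI and PCL-C, standard forms | x | | x | | x |
| GAD-7, standard form | | | x | | x |
| GAD-7, since last collection | | x | | x | |
| FSS | x | x | x | x | x |
| CES-D | | x | x | x | x |

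The rows set out here for the standard forms, the GAD-7, the FSS and the CES-D each contain all 14 cells, so a shifted column does not explain the blanks. Compared with "PTSD Checklist for Civilians (PCL-C) - Standard", the GAD-7 standard row is identical except for V1. Compared with FSS, the CES-D row is identical except for V1.

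**3. The other rows.** Thirteen repeated measures keep a V1 mark: PSS, ISI, PCL-C, FSS, QOLS, ISEL-12, MASQ, DASS-21, EQ-5D, HPQ, healthcare utilization, the COVID questions and HRV. The barriers survey has none, but the text says it is collected only at V3 and V5.

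**4. What the text needs.**

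- *GAD-7.* A V1-to-V3 change is V3 minus V1. With V1 blank, the difference is undefined for every participant whose form followed the schedule. No passage names the GAD-7 at V1, so its baseline rests on general statements only.
- *CES-D at V1.* The check above 35 uses a V1 score that the schedule does not provide.
- *CES-D increase.* A rise of 10 points or more needs an earlier score. At V2, the first follow-up, the schedule offers none. From V3 on, V2 could serve, but in the early arm V2 falls after the intervention. The text explains the 10-point figure by reference to change from baseline in the exploratory study.

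**5. Possible substitutes.** The DASS-21 is marked at V1 and has anxiety and depression subscales, but it is a different instrument and cannot supply a GAD-7 or CES-D change. In the delayed arm, V2 and V3 precede crossover, but they do not provide the V1 value for the randomised comparison.

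**The case against.** The strongest reply is that nothing is missing from the plan.

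*The table may have been misread.* Its group header is broken in mid-word, and the marks mix Latin and Cyrillic letters, which fits character-by-character recognition without proving it. The two blanks that matter are vertically adjacent cells in one column, so one local loss could account for both. The cell count excludes a column shift but not a dropped mark. This stands: only the original page can settle it.

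*The text shows the intent.* The CES-D passage speaks of the V1 survey in so many words. The Abstract has symptom questionnaires collected at V1, and the section on number of sessions and length of study places all baseline measures at enrolment. V2 is described as a repeat of the measures, and Appendix A lists both scales. The same team's exploratory study had V1 values on both for all 103 participants (Table 1). This also stands, more firmly for the CES-D than for the GAD-7. The V2 wording of the GAD-7 form adds little, because it fixes a recall period and does not say that the scale was given at V1.

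*The consequence is limited.* Arms could still be compared on GAD-7 at V3, and randomisation would support that comparison. That is correct, but it is not the change analysis that the plan describes.

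A reader might infer from the schedule that the trial has no baseline for either scale, or that all such baselines are lost. The documents do not support this. The text contradicts it directly for the CES-D and by implication for the GAD-7, and nothing in the documents shows what the V1 form contained. Nor is there any sign that someone chose to omit a baseline.

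What survives is that the operative table, as it reads, disagrees with the text, and that general wording which names no instruments does not correct it.

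**Conclusion.** The inconsistency is real in the schedule as read: no V1 mark for one of two secondary outcomes, and none for the scale behind two stated CES-D rules. It is a disagreement between schedule and text, not a design decision.

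Its practical effect depends on two conditions that the documents cannot settle: that the original cells are blank, and that the V1 form was built from them. If both hold, the planned GAD-7 change cannot be computed, the V1 CES-D check has no score to act on, and the increase rule has no reference at V2. If either fails, no data are affected. The documents give no basis for a figure between these two outcomes, so none is offered. The point merits correction because a lost baseline could not be recovered and the check is almost free.

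**What to change.** 1. Look at the V1 column of the original Schedule of Activities for the GAD-7 standard row and the CES-D row.
2. If the cells are blank, mark V1 in both, so that the schedule agrees with the Abstract, the enrolment and session-timing text, the CES-D paragraph, the Analytical Plan and the safety text.
3. Whatever the table shows, confirm that the V1 REDCap form contains both scales.
4. If the form did omit the GAD-7 for some participants, record how many, and state that the V1-to-V3 change cannot be computed for them.

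The cost is at most two table cells and one check of the electronic form. If the scales were absent from it, adding them takes a few minutes per participant. No threshold or clinical rule needs to change; the passages only need to be reconciled.
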